### 1.4.4 Discussion

Based on pre-clinical and clinical results, BI 3011441 showed single agent anti-tumour activity in a xenograft mouse model as well as in subjects with RAS mutant solid tumours. The therapeutic benefit or specific adverse events in patients cannot always be anticipated during the trial setup and therefore, patients should be advised and carefully monitored for the potential risk of side effects from this investigational drug.

The clinical trial sites qualified to participate in this trial will be experienced comprehensive cancer centres in treating patients with investigational drugs and with the necessary infrastructure. The Investigators and Sponsor will form a SMC. During the conduct of trial, the SMC will meet regularly and during dose escalation at minimum after all patients in each dose cohort have completed cycle 1. The Sponsor will continuously assess the risks and benefits of the trial based on accumulating clinical data from all clinical trials with BI 3011441. Any significant change in risk/benefit ratio will be communicated to Investigators and patients.

In summary, the present trial will implement a number of safety measures to mitigate possible risks. Therefore, a potential benefit is offered to patients with advanced and/or metastatic malignancies with no other approved treatment options with BI 3011441. The benefit-risk ratio of treating patients with BI 3011441 monotherapy is therefore considered to be acceptable.

## 2. TRIAL OBJECTIVES AND ENDPOINTS

### 2.1 MAIN OBJECTIVES, PRIMARY AND SECONDARY ENDPOINTS

#### 2.1.1 Main objectives

The primary objective of this trial is to confirm the safety and tolerability of previously identified MTD, BI 3011441 8mg (in Caucasian FIH study) as a single agent when administered orally to adult Japanese patients with NRAS/KRAS mutation positive advanced or metastatic refractory solid tumours.

The MTD will be determined based on the frequency of patients experiencing DLTs during the MTD evaluation period. The MTD evaluation period is defined as first treatment cycle (28 days). At the end of the dose escalation, the BLRM will be rerun using all DLTs. This result as well as all available data will be used to define the recommended dose (RD).

The secondary objectives is to evaluate the safety and tolerability, and characterise PK of BI 3011441 as monotherapy in Japanese patients with NRAS/KRAS mutation positive advanced solid tumours

#### 2.1.2 Primary endpoint(s)

- MTD defined as the highest dose with less than 25% risk of the true DLT rate being equal or above 33% during the MTD evaluation period. For the definition of DLTs, refer to [Section 5.2.6.3](#)
- Number of patients with DLTs in the MTD evaluation period.

#### 2.1.3 Secondary endpoint(s)

- Number of patients with DLTs during the entire on-treatment period
- Number of patients with Grade  $\geq 3$  treatment-related adverse events
- Number of patients with treatment related adverse events at each dose level
- Pharmacokinetic parameters of BI 3011441:  $C_{max(ss)}$ , and  $AUC_{0-tz(ss)}$

### 3. DESCRIPTION OF DESIGN AND TRIAL POPULATION

#### 3.1 OVERALL TRIAL DESIGN

The trial is an open-label, non-randomised phase I trial of BI 3011441 as monotherapy to investigate the safety/tolerability, PD and PK profile at selected dose levels in Japanese patients with NRAS/KRAS mutation positive advanced or metastatic refractory solid tumours. Patients will be enrolled based on the available NRAS/KRAS mutation status previously identified by local test results performed prior to screening. The data obtained from the trial will determine the MTD estimate based on a Bayesian logistic regression model with overdose control ([R13-4803](#)). The BLRM estimates the MTD by updating estimates of the probability of observing a DLT in the MTD evaluation period for each dose level in the trial as patient information becomes available. At any time in the trial, it will not be permitted to escalate to a dose which does not fulfil the escalation with overdose control (EWOC) principle (refer to [Section 7](#)).

The provisional dose levels to be evaluated will be 4mg, 6mg and 8mg, which includes the previously established MTD of 8mg for Caucasian patients. For any dose-escalation cohort, at least 3 patients will be required (refer to Section 7). However, in the case that only 2 patients are evaluable and neither has experienced a DLT within the MTD evaluation period, then dose-escalation can occur based on these 2 patients. For determination of MTD or RD, 6 patients will be enrolled at least. A BLRM with overdose control will be performed once the enrolment of 3 patients at each dose level has been completed and these patients completed the first cycle of treatment of BI 3011441. Each cycle will consist of 28 days (4 weeks) and patients will continue the treatment until undue drug toxicity, disease progression, or withdrawal of consent, whichever occurs first. The longest treatment period will be 2 years if deemed safe and efficacious. Intra-patient dose escalation will be allowed if there is an indication from higher-dose cohorts that there is a positive-risk-benefit once the patient completed the 1st cycle of treatment including PK sampling.

[figure not shown]

Figure 3.1: 1

Study design

The Safety Monitoring Committee (SMC, see [Section 8.7](#)) will recommend the size for the next dose escalation cohort. After all patients in a cohort have either experienced a DLT or have been observed for at least the MTD evaluation period without experiencing a DLT, the Bayesian model will be updated with the newly accumulated data. The overdose risk will then be calculated for each dose, and escalation will be permitted to all doses which fulfil the EWOC criterion and the additional 50 % escalation rule. Based on the model and on

Proprietary confidential information © 2020 Boehringer Ingelheim International GmbH or one or more of its affiliated companies

additional information (PK, PD, patient profiles), the members of the SMC will reach a joint decision on the next dose level to be investigated.

If DLTs are observed in the first two consecutive patients of a previously untested dose level, subsequent enrolment to that cohort will be stopped. The BLRM will be re-run to confirm that the dose level still fulfils the EWOC principle. Based on this information, the SMC will evaluate whether the next patients will be enrolled at the same dose level, or if they will be enrolled at a lower dose level.

The SMC may recommend stopping the dose escalation phase after the criterion for MTD ([Section 7.1](#)) is fulfilled. Further patients may be included to confirm this MTD estimate, i.e. to confirm that the EWOC criterion is still fulfilled. If no DLT is observed at a dose of which the efficacy is considered sufficient, the SMC may decide to include an additional number of patients at the same dose level and to declare this dose as the recommended.

The SMC can declare any dose fulfilling the EWOC criterion as the RD, independent of the MTD estimate.

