- c) Physical examinations including the measurements of height (screening only) and weight will be done at screening, on Day 1 of each treatment cycle, at the end-of-treatment (EOT) visit, at the 30-day end of residual effect (EOR) visit, and at the follow-up (FU) visits for progressive disease. ECOG performance status will be done at screening, on Days 1 and 15 of Cycle 1, Day 1 of Cycle 2, on Day 1 of every other cycle beginning with Cycle 3, at the EOT visit, at EOR, and at FU visits for progressive disease.
- d) A patient diary will be given to the patient for continuous use through the trial. It should be given to the patient at the start of each cycle. The diary collects information about BI 3011441 taken at home and provides reminders about fasting blood samples. After one week on trial medication, treatment compliance should be discussed with the patient, to ensure that the medication is being taken correctly (no compliance calculation has to be performed). Then at Visit 1 of each cycle and at EOT treatment compliance needs to be checked including compliance calculations.
- e) 12-lead electrocardiograms (ECGs) will be done in triplicate before blood work or other procedures after 5 minutes of rest at screening, see [section 5.2.4](#).
- f) LVEF is measured by echocardiography at screening, Day 15 of Cycle 1, C2V1, then every 2 cycles (i.e. C4V1, C6V1, C8V1, etc.) and EOT. Additional LVEF assessments should also be done if clinically indicated.
- g) Safety laboratory assessments including haematology, serum biochemistry, coagulation, pregnancy tests, urinalysis and virology (only at screening) will be performed locally. If screening laboratory tests are completed within 72 hours prior to first dose, predose samples on Day 1 of Cycle 1 will not be repeated. See [Section 5.2.3](#) for further detail. Pregnancy tests are mandatory for women with child-bearing potential. A serum beta human chorionic gonadotropin ( $\beta$ -HCG) pregnancy test must be done at screening. Thereafter, this test can be done in either serum or urine on Day 1 of each cycle, at the EOT visit, and at EOR.
- h) An ophthalmological assessment must be done at screening, C2V1, C3V1, C4V1 and then every 2 cycles (i.e. C6V1, C8V1, C10V1, etc.) and EOT. Ophthalmological assessment can be done separated  $\pm 2$  day from visit. Additional ophthalmological assessments should also be done if clinically indicated.

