#### 5.2.6.3 Dose limiting toxicities

DLTs will be recorded throughout the trial. Any DLT must be reported to the Sponsor by the Investigator or designee within 24 hours of first knowledge using the same procedure as SAE reporting. Only DLTs occurring in the first 4 weeks (the first cycle) of treatment are considered for dose-escalation decisions made by the SMC. DLTs observed during the MTD

Proprietary confidential information © 2020 Boehringer Ingelheim International GmbH or one or more of its affiliated companies

evaluation period will be considered for MTD determination. In addition, DLT(s) observed during the ophthalmological assessment and echocardiographic assessment of Cycle 2 Day 1 will be considered for MTD determination. However, all AEs and SAEs meeting criteria of DLT observed in all treatment cycles will be considered for determining a RD.

Any of the following AEs will be classified as DLTs if assessed as possibly related to BI 3011441, i.e., unless unequivocally due to underlying malignancy or an extraneous cause and will be reviewed by the SMC.

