  - After holding the trial drug and obtaining a follow-up echocardiography within 4 weeks, LVEF has returned within the normal institutional range or to within 5 percentage points of the screening value, but on re-challenge there is second decline of an absolute decrease in LVEF of 10 percentage points or greater from screening value, whether above or below institutional LLN.
- Symptomatic heart failure
- Any retinopathy  $\geq$  Grade 2
- Retinal vein occlusion of any grade.
- Interstitial lung disease/pneumonitis of any grade
- Hepatic injuries assessed as related to trial drug and which meet the AESI criteria for hepatic injury in [Section 5.2.6.1.4](#)
- Treatment pause of BI 3011441 for  $\geq$ 14 days, or dose reduction in Cycle 1 due to treatment-related AEs
- Any treatment-related  $\geq$  Grade 2 toxicity that persists and results in a more than 2 weeks delay of administration of BI 3011441 on Cycle 2 Day 1
- Any treatment-related AE that would require permanent discontinuation of BI 3011441.

Any other toxicity considered significant enough to be qualified as DLT in the opinion of the Investigators, and confirmed by the SMC, will be reported as a DLT.

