## 10.2 STATISTICAL APPENDIX INCLUDING MODEL PERFORMANCE AND DATA SCENARIOS

A Bayesian logistic regression model with overdose control will be used to guide dose escalation in this trial. The BLRM is introduced in [Section 7.1](#), which also specifies the prior for the model. After patients in each cohort have completed at least one cycle of treatment, the prior distribution will be updated through Gibbs sampling procedures with the accumulated DLT data from the MTD evaluation period. Posterior probabilities for the rate of DLTs will be summarised from BLRM. Selection of the next dose will be based on these probabilities as well as on other safety and laboratory data.

The purpose of this statistical appendix is to present performance metrics (operating characteristics) that illustrate the precision of the design in estimating the MTD under various dose-toxicity relationships through computer simulation. These results are summarized in [Table 10.2:3](#). In addition, recommendations of the next dose level by the BLRM with overdose control principle are also provided under various hypothetical outcome scenarios in early cohorts to show how it facilitates on-trial dose-escalation decisions (see [Table 10.2:1](#)). For simplicity reasons, a cohort size of 3 patients who are all evaluable is assumed.

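### A retinal DLT first found at the Cycle 2 Day 1 eye examination counts towards the MTD but, as written, can be left out of the escalation model, where one such event reverses the decision.

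*Protocol*

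**What the plan says.** **When the model is updated.** Protocol Section 2.1.1 sets the MTD evaluation period as Cycle 1, 28 days. Section 3.1 updates the model after all patients in a cohort have had a DLT or "have been observed for at least the MTD evaluation period without experiencing a DLT, the Bayesian model will be updated". Appendix 10.2 says: "After patients in each cohort have completed at least one cycle of treatment, the prior distribution will be updated". Section 1.4.4 has the safety monitoring committee (SMC) meet "during dose escalation at minimum after all patients in each dose cohort have completed cycle 1". None of these requires an eye examination result first.

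**Which DLTs count.** Section 5.2.6.3 states: "Only DLTs occurring in the first 4 weeks (the first cycle) of treatment are considered for dose-escalation decisions made by the SMC". It then adds that DLTs observed "during the ophthalmological assessment and echocardiographic assessment of Cycle 2 Day 1 will be considered for MTD determination".

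**When the eye is examined.** Flow Chart footnote h: "An ophthalmological assessment must be done at screening, C2V1, C3V1, C4V1 and then every 2 cycles". The Cycle 2 visit has a window of ±2 days, and the examination may be a further ±2 days from the visit. Unscheduled examinations are allowed when clinically indicated.

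**What is a DLT.** The Section 5.2.6.3 list includes retinopathy of Grade 2 or higher and "Retinal vein occlusion of any grade". The historical data behind the main prior component (Table 7.1:1) were recoded to count Grade 2 retinopathy.

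**SAP.** Table 6.1: 1 ends the MTD evaluation period at first dose + 28 days. Sections 7.4.1 and 7.8.1.1 call it the first treatment cycle. None of the three mentions the Cycle 2 Day 1 addition.

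**The concern.** Sections 3.1 and 7.1 describe one model and one overdose criterion (EWOC), serving both the escalation steps and the MTD. Section 5.2.6.3 appears to feed that model two different DLT counts for the same patients. The difference falls on ocular toxicity, which Table 1.4.2:1 lists as seen in the first-in-human study and which the prior was recoded to include. The first routine look for silent retinal change comes, at nominal timing, one day after the earliest point at which the cohort can be closed.

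EWOC limits overdose risk only for the events in the data. If a silent retinal DLT is scored as no DLT at an escalation step, the posterior that opens the next dose is too favourable compared with the one later used for the MTD. Cohorts hold about 3 patients, so one misclassified patient carries great weight.

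**Working it through.** **1. Timing.** The Cycle 2 visit is nominally Day 29. The visit window gives Day 27 to 31, and the examination window then gives Day 25 to 33. The earliest model update is at the end of Day 28. The examination can therefore come up to 33 − 28 = 5 days after it, and nominally 29 − 28 = 1 day after it.

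**2. Model.** From Section 7.1 and Table 7.1:2: logit(π_d) = log(α) + β·log(d/8), with θ = (log α, log β). The prior is a three-component normal mixture:

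| Component | Weight | Mean | SD | Correlation |
|---|---|---|---|---|
| MAP | 0.8 | (−0.94, 0.61) | (0.91, 0.91) | −0.08 |
| High toxicity | 0.1 | (0.85, 0.79) | (2, 1) | 0 |
| Low toxicity | 0.1 | (−2.20, 0.80) | (2, 1) | 0 |

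The likelihood is binomial at each dose. P(OD) is the posterior probability that π_d ≥ 0.33, and a dose passes EWOC if P(OD) < 0.25. The posterior was found by numerical integration on a grid.

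**3. Reproducing the plan's figures.** Prior P(OD) at 4, 6, 7 and 8 mg is 0.129, 0.232, 0.310 and 0.421. Table 7.1:3 gives 0.128, 0.233, 0.310 and 0.422. Against Table 10.2:1:

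| Scenario | Data | P(OD) compared | Plan | Recomputed | Plan's next dose |
|---|---|---|---|---|---|
| 1 | 4 mg 0/3 | current, 4 mg | 0.026 | 0.026 | 6 mg |
| 2 | 4 mg 1/3 | current, 4 mg | 0.194 | 0.206 | 4 mg |
| 6 | 4 mg 0/3, 6 mg 0/3 | next, 8 mg | 0.185 | 0.196 | 8 mg |
| 7 | 4 mg 0/3, 6 mg 1/3 | current, 6 mg | 0.153 | 0.148 | 6 mg |

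The largest difference is 0.206 − 0.194 = 0.012, and all four recommended doses agree once the 50% increment cap is applied.

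**4. Recoding one patient from no DLT to DLT.**

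| Step | Dose considered | P(OD), event left out | P(OD), event counted | Against 0.25 |
|---|---|---|---|---|
| After 3 patients at 4 mg | 6 mg | 0.094 (0/3) | 0.403 (1/3) | passes, then fails |
| After 0/3 at 4 mg and 3 patients at 6 mg | 7 mg | 0.074 (0/3) | 0.276 (1/3) | passes, then fails |
| Same | 8 mg | 0.196 (0/3) | 0.43 (1/3) | passes, then fails |

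The reversal does not depend on the recomputation. The plan's own scenarios 1 and 2, and 6 and 7, already show go to 6 mg against stay at 4 mg, and go to 8 mg against stay at 6 mg.

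Under the Section 3.1 allowance to escalate on 2 evaluable patients without a DLT, 0/2 at 4 mg gives P(OD) 0.122 at 6 mg. If one of the two is recoded, 4 mg itself fails at 0.301.

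**5. How often.** The documents give no rate for retinal DLTs first detected at this examination. For an assumed per-patient rate p, the chance of at least one in a cohort of 3 is 1 − (1 − p)³:

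| p | Chance of at least one |
|---|---|
| 2% | 1 − 0.98³ = 0.059 |
| 5% | 1 − 0.95³ = 0.143 |
| 10% | 1 − 0.90³ = 0.271 |
| 20% | 1 − 0.80³ = 0.488 |

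**The case against.** **Day 28 is a minimum.** A reader might infer that the update always runs on Day 28. Sections 3.1, 10.2 and 1.4.4 all set a lower bound, so the SMC may wait, and patients enrolled earlier in the cohort may already have been examined. This stands. But waiting is optional, and a late finding would still meet the first-4-weeks sentence.

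**Most retinal events are caught.** A reader might infer that all retinal DLTs are missed. They are not. Symptomatic events in Cycle 1 lead to an unscheduled examination, Table 4.1.4.2: 2 requires immediate referral even for Grade 1 retinopathy, and examinations on Days 25 to 28 fall inside the cut. What remains is mainly silent DLTs first found after Day 28.

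**The SMC sees more than the model.** Section 4.1.2 has the SMC discuss data beyond the evaluation period on other ongoing patients before choosing the next dose, and Section 4.1.4 lets later AE information inform dose assignment. DLTs are reported within 24 hours, and Section 3.3.4.1.1 allows enrolment to be halted. So the inference that a late-found DLT stays out of view until the MTD is declared, after the next cohort has been dosed, is not supported. These routes rest on judgement, however. They do not put the event into the BLRM or EWOC, which Section 3.1 makes the binding limit. The Section 4.1.4.1 requirement for a clear eye examination before a new cycle protects the patient already treated, not the next cohort.

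**The wording may be meant more broadly.** Sections 3.3.4.1.2 and 4.2.2.1 call the first 4 weeks the MTD determination period, and the former links MTD evaluability to escalation decisions, so MTD determination might include cohort updates. A finding observed at Cycle 2 Day 1 might also be held to have occurred in Cycle 1. Both readings are possible and neither is stated, so the two-count reading is the literal one rather than a certain one.

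**No firm share of late examinations.** If visit and examination days were uniform over their windows, 15/25 = 60% of examinations would fall after Day 28. Only 10/25 = 40% would fall after Day 29, where the SAP's first dose + 28 days ends (SAP Section 6.7 counts first dose as Day 1). Uniform timing has no basis in the documents, so neither figure is relied on here.

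**Conclusion.** The concern holds in this limited form. Followed literally, the plan can score a retinal DLT first found after Day 28 as no DLT in the escalation model and as a DLT for the MTD. Nothing in either document makes the cohort update wait for the examination, and the protocol and SAP do not agree on where the evaluation period ends.

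When such an event occurs, the effect is decisive. A single one moves P(OD) for the next dose from below 0.25 to well above it at both the 4 mg and the 6 mg step. How often that would happen is unknown: about 6% to 49% per cohort of 3 for assumed rates of 2% to 20%. The size rests on the Section 7.1 model and prior, on cohorts of 3 with all patients evaluable, and on the update being run without the finding. The documents do not show that this will happen in every cohort, or that the SMC would be unaware of the event. This should be corrected, because the safeguard that remains is discretionary while EWOC is meant to be binding.

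**What to change.** Reconcile Protocol Sections 3.1, 5.2.6.3 and 10.2 with SAP Table 6.1: 1 and SAP Sections 7.4.1 and 7.8.1.1, as follows:

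- **One DLT data set.** State in Section 5.2.6.3 that DLTs observed at the Cycle 2 Day 1 eye and echocardiography assessments enter the BLRM for escalation decisions as well as for MTD determination. Where an end-of-treatment visit replaces that visit, its eye and echocardiography assessments serve the same purpose.
- **One trigger.** In Sections 3.1 and 10.2, run the cohort update once every patient has had a DLT, or has completed the MTD evaluation period with those results available, or is no longer evaluable.
- **SAP.** Give the evaluation period one end point consistent with the protocol, and carry over the Cycle 2 Day 1 addition.

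The cost is protocol and SAP wording plus a wait of about 1 day per cohort at nominal timing and up to about 5 days within the permitted windows. The wait may be longer where an end-of-treatment visit replaces the Cycle 2 visit. No procedure, patient, dose or DLT criterion is added or changed.

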### **3.2 DISCUSSION OF TRIAL DESIGN, INCLUDING THE CHOICE OF CONTROL GROUP(S)**

The clinical data of BI 3011441 from the FIH study conducted in Caucasian patients allows to already define three dose levels to be investigated in this trial.

Although provisional dose levels exist, dose escalation and cohort size will be still determined based on the recommendation of the SMC, guided by a BLRM with overdose control. An escalation with overdose control design will increase the chance of treating patients at efficacious doses while reducing the risk of overdosing. This design is based on practical experience and is an efficient method due to its ability to identify the dose with a desired toxicity rate and its allocation of a greater proportion of patients to doses at, or close to, that desired dose ([R13-4802](#), [R13-4804](#), [R13-4805](#)). The use of Bayesian models for Phase I studies has also been advocated by the EMA guideline on small populations ([R07-4856](#)) and by the FDA ([R13-4881](#)). This trial is a single-arm trial with multiple dose cohorts and there is no control group.

